Edition Number: **4**

Date: **11 February 2022**

- To evaluate the efficacy of sirolimus followed by durvalumab as neoadjuvant treatment for Stage I, II, and IIIA NSCLC

Secondary Objective(s):

- To evaluate the efficacy of sirolimus followed by durvalumab as neoadjuvant treatment for Stage I, II, and IIIA NSCLC
- To evaluate response to sirolimus followed by durvalumab in patients with PD-L1 positive vs. PD-L1-negative tumors
- To evaluate the association between blood mutation burden and response to sirolimus followed by durvalumab

Exploratory Objective(s):

- To evaluate the immune-mediated effects of sirolimus followed by durvalumab
- To investigate tumor and immune microenvironment changes in tissue samples

Study Design:

Up to 31 patients with NSCLC will be enrolled in this study at Emory University Winship Cancer Institute and associated clinical sites. Eligible patients will complete 3 weeks of daily oral sirolimus followed by 2 cycles of durvalumab treatment prior to proceeding to standard of care surgical resection. Durvalumab will be administered at a dose of 1500mg Q 3 weeks starting on C1D1 for up to 2 cycles that are 21 days in length. Pharmacodynamic analysis will be done using PD samples collected at baseline (tissue) and with blood samples on day 1, day 22 C1 prior to durvalumab, day 43 C2 durvalumab, and at the time of surgery (blood and tissue). Additional post surgery blood samples will be collected at 1-, 3-, and 6-months post-surgery. See Appendix D for schedule of Biomarker collection. Patients will proceed to surgery within a 2–3-week period post 2nd dose of durvalumab but not earlier than two weeks after the administration of durvalumab i.e. not earlier than C2D14. Additionally, as an optional study, patients will self-administer heavy water (D2O) 50ml orally three times a day from day 22 C1 through day 27 followed by 50ml orally twice a day through the day prior to surgery in order to label dividing cells for research tracking purposes.

Number of Centers: Emory University Winship Cancer Institute and affiliated hospitals

Number of Patients: 31

Study Population: Resectable Stage 1-3A NSCLC

Inclusion Criteria:

- Pathologically documented NSCLC who are candidates for surgical resection
- Capable of signing informed consent

- Age \geq 18 years at time of study entry.
- Eastern Cooperative Oncology Group (ECOG) performance status of 0 or 1
- Life expectancy of \geq 26 weeks
- Body weight >30 kg

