- Judgment by the investigator that the patient is unsuitable to participate in the study and the patient is unlikely to comply with study procedures, restrictions and requirements.

Investigational Product(s), Dose and Mode of Administration:

Patients will receive 1500 mg durvalumab via IV infusion Q3W for up to a maximum of 2 cycles prior to curative resection surgery. Weight-based dosing (20 mg/kg) should be utilized for patients whose body weight falls to <30 kg while on study.

Patient will self-administer sirolimus 6 mg orally once on day 1, followed by once daily dosing of 2mg, continuously through day 21, which is one day prior to C1 of durvalumab. The dose should be taken each morning, with or without food.

Study Assessments and Criteria for Evaluation:

Safety Assessments:

- Incidence of adverse events, with severity per NCI CTCAE v5.0
- Length of hospital stay after surgery

Efficacy Assessments:

- Complete pathologic response, scored by a pathologist, based on surgical resection as defined by prior studies
- Investigator-assessed response rate per RECIST v1.1
- DFS and OS
- Pathological response in PD-L1-positive and PD-L1-negative groups
- Overall response rate in PD-L1-positive and PD-L1-negative groups based on mutational burden

Statistical Methods and Data Analysis:

Safety Analyses:

All enrolled patients will be evaluable for safety analyses from the time of their first treatment with sirolimus. After study complete, DLTs will be summarized and tabulated by type and grade. DLT rate

by dose level will be calculated as proportion (Patients with DLT/Total patients) along with 95% confidence intervals using the Clopper-Pearson method. Chi-square test or Fisher's exact test will be used to compare the probability of DLT between the different other factors, such as PD-L1 status, dose levels, etc. respectively.

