	Screening	Sirolimus	Durvalumab C1	Durvalumab C2	Pre- surgery	Surgery	Study DC	Follow- up	For details see Section	
Week	-4 to 0	0	3	6	8-9		Post Surgery 30 +/- 7 days	Every 3 months for 2 years		
Day	-28 to 0	1-21	22 +/- 3 days^a	43 +/- 3 days^a	57-64 +/- 10 days					
Tumor biopsy (newly acquired/fresh if amenable to core biopsy)	X								Error! Reference source not found. Error! Reference source not found.	
Tumor biopsy (archival, required for diagnosis and PD-L1 assessment)	X								Error! Reference source not found.	
Fresh tumor and lymph node samples for immunologic analysis						X				
Efficacy evaluations										

Clinical Study Protocol

Drug Substance Sirolimus (Rapamune)

Study Number **19-20015**

Edition Number: **4**

Date: **11 February 2022**

	Screening	Sirolimus	Durvalumab C1		Durvalumab C2		Pre- surgery	Surgery	Study DC	Follow- up	For details see Section	
Week	-4 to 0	0	3		6		8-9		Post Surgery 30 +/- 7 days	Every 3 months for 2 years		
Day	-28 to 0	1-21	22 +/- 3 days^a		43 +/- 3 days^a		57-64 +/- 10 days					
Tumor evaluation (CT or MRI) (RECIST 1.1) ¹ within 6 weeks of C1D1	X ^b						X				Error! Referen ce source not found.	
Pathologic response assessment								X				

^a If cycle 2 day 1 visit is delayed, all subsequent visits will be delayed accordingly

^b Informed consent of study procedures and tumor biopsy sample may be obtained prior to the 28-day screening window, if necessary, in order to permit tumor biopsy sample acquisition and analysis prior to randomization. The collection of tumor biopsies at the time of progression prior to retreatment is mandated; the Investigator must consult with the Study Physician if such sampling is not feasible. If laboratory or imaging procedures were performed for alternate reasons prior to signing consent, these can be used for screening purposes with consent of the patient. However, all screening laboratory and imaging results must have been obtained within 28 days of study assignment.

^c Body weight is recorded at each visit along with vital signs

^d Any clinically significant abnormalities detected require triplicate ECG results.

^e Serum or plasma clinical chemistry (including LFT monitoring) and hematology may be performed more frequently if clinically indicated.

^f If screening clinical chemistry and haematology assessments are performed within 3 days prior to Day 1 (first infusion day), they do not need to be repeated at Day 1.

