3. STUDY DESIGN

3.1 Overview of study design

This is a Phase Ib open-label, single-arm study in newly diagnosed stage I-IIIA NSCLC patients, to test sirolimus in combination with durvalumab as neoadjuvant treatment prior to curative-intent surgical resection. The safety and tolerability as well as efficacy of combination sirolimus with durvalumab will be evaluated in this treatment setting. The study is also designed to investigate a number of laboratory correlative studies to define mechanisms of anti-tumor activity of sirolimus + durvalumab and several potential predictive biomarkers, which will help identify patients who are more likely to respond to treatment. Finally, the study will also include DFS and OS as secondary endpoints.

Up to 31 patients with NSCLC will be enrolled in this study at Emory University Winship Cancer Institute and affiliated sites. Enrollment will occur in 2 parts based on Simon 2 stage design, in which at least 2 of the first 16 patients must achieve pathologic complete response in order for the study to enroll 15 additional patients.

Eligible patients will complete 2 cycles of outpatient study treatment prior to proceeding to standard of care surgical resection. In order to allow a reliable assessment of the contribution of sirolimus versus durvalumab to the observed clinical and PD outcome, treatment will start with sirolimus 6mg orally for one loading dose followed by 2mg orally once daily three weeks prior to the start of durvalumab. Durvalumab will be administered at a dose of 1500mg Q 3 weeks starting on C1D1 for up to 2 cycles that are 21 days in length. Pharmacodynamic analysis will be done using PD samples collected at baseline (tissue) and with blood samples on day -7, C1D1 prior to durvalumab, C1D8, C2D1, C2D8 and at the time of surgery (blood and tissue). Additional post surgery blood samples will be collected at 1, 3, and 6 months post-surgery. See **study schedule of assessments** for schedule of Biomarker collection. Patients will proceed to surgery within a 4-week period post 2nd dose of durvalumab but not earlier than one week after the administration of durvalumab i.e. not earlier than C2D8. Additionally, patients will self-administer heavy water (D2O) 50ml orally three times a day from C1D1 through C1D5 followed by 50ml orally twice a day through the day prior to surgery in order to label dividing cells for research tracking purposes.

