5.1.2 Durvalumab doses and treatment regimens

Regimen Description					
Agent	Premedications Precautions	Dose	Route	Schedule	Cycle Length
Durvalumab	None required	1500 mg in NS or D5W	IV over 1 hr	Once every 3 weeks, starting on day 22	21 days (3 weeks)

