8. STUDY PROCEDURES

8.1 Schedule of study procedures

Before study entry, throughout the study, and following study drug discontinuation, various clinical and diagnostic laboratory evaluations are outlined. The purpose of obtaining these detailed measurements is to ensure adequate safety and tolerability assessments. Clinical evaluations and laboratory studies may be repeated more frequently if clinically indicated. The Schedules of Assessments during the screening and treatment period is provided following the Protocol Synopsis.

- Tumor efficacy (RECIST) assessment dates are not affected by dose delays and remain as originally scheduled, as they are based on the date of surgery.
- All other scheduled assessments must be performed relative to the start of the dosing cycle such that all laboratory procedures, etc. required for dosing should be performed within 3 days prior to dosing.
- Patients may delay durvalumab dosing under certain circumstances.
 - Dosing may be delayed per Toxicity Management Guidelines, due to either an immune or a non-immune-related AE.
 - If dosing must be delayed for reasons other than treatment-related toxicity, dosing will resume as soon as feasible

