8.1.2 Treatment phase

Procedures to be conducted during the treatment phase of the study are presented in the Schedule of Assessments. Screening procedures performed within 72 hours of cycle 1 day 1 do not need to be repeated on cycle 1 day 1.

1. Sirolimus dosing: will be given 6mg po once on day 1, followed by 2mg po daily on days 2-21. Steady state trough levels will be collected on day 23 and stored for batch analysis.
2. Heavy water dosing: first dose to be taken in clinic on day 23 and a 6 week supply for self- administration will be dispensed in labeled conical tubes. The patients will also be shown how to collect salivate samples.
3. Durvalumab dosing: starting on Day 22 q 3 weeks for 2 doses
4. Restaging imaging prior to surgery
5. Standard of care surgical resection
6. Peripheral blood research tube collection per study calendar

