8.2.3 Sirolimus Level Collection

Sirolimus levels should be collected as troughs to facilitate intra-patient comparison.

Step 1: The level is scheduled to be drawn on day 22, which is C1D1 Durvalumab and the last dose is on day 21. Therefore this timing should be appropriate for trough level. If there are anticipate delays in durvalumab, then appointment should be made for this lab draw. The coordinator should call the patient 1-2 days before the appointment to remind them about trough level and for patient to bring that am dose to clinic.

Step 2: Collection Tube details:

Whole Blood (EDTA): One 5 mL lavender (EDTA) tube. Minimum volume needed 250 μ L whole blood (EDTA), single test, with no repeat.

Step 3: Specimen Preparation: Whole blood. Do not spin. Samples obtained from Winship (either at Emory University or other site such as Emory St. Joseph's Hospital) should be submitted the same day to special chemistry lab. Samples obtained at Grady should be be couriered over to Winship at [name] for analysis (along with the CPT tube for immunologic analysis).

- Unacceptable conditions include serum or plasma collection or clotted specimens and will be discarded. Patient should be scheduled for repeat lab
- Storage/Transport Temperature
Stable at room temperature, 15-30°C for up to 7 days. Stable refrigerated at 2-8°C for up to 14 days.
- Performed only on day shift. Must be in Special Chemistry lab by 13:00 pm M-F and 11:00 am on weekends and holidays for same day results.

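### The printed visit windows allow durvalumab to start before the day 22 set by the dosing text, and allow the two infusions to be 15 days apart instead of 21

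*Combined protocol and SAP*

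**What the plan says.** Two parts of the combined protocol and SAP set the date of the infusions.

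**Dosing text.** The synopsis (Investigational Product(s), Dose and Mode of Administration) has sirolimus taken "continuously through day 21, which is one day prior to C1 of durvalumab". The synopsis study design gives durvalumab at "1500mg Q 3 weeks starting on C1D1 for up to 2 cycles that are 21 days in length". Section 5.1.2 has "Once every 3 weeks, starting on day 22", and Section 8.1.2 has "Durvalumab dosing: starting on Day 22 q 3 weeks for 2 doses". Section 8.2.3 uses the same calendar for the trough: "The level is scheduled to be drawn on day 22, which is C1D1 Durvalumab and the last dose is on day 21". None of these places gives a tolerance.

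**Visit schedule.** The Day row of the Schedule of Study Assessments lists sirolimus as days 1–21, C1 as day 22 ± 3 and C2 as day 43 ± 3. Footnote a is marked on both infusion cells: "If cycle 2 day 1 visit is delayed, all subsequent visits will be delayed accordingly".

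Section 8.1 allows durvalumab to be delayed and adds "All other scheduled assessments must be performed relative to the start of the dosing cycle". That governs assessments. It does not set the date of the second infusion.

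**The concern.** A symmetric window around day 22 overlaps the sirolimus course on its early side. A window around day 43 that is counted from sirolimus day 1 lets the gap between infusions vary with both visit dates. The dosing text permits neither, and nothing in the supplied text says which part governs. An infusion on day 20 is in window by the schedule and a deviation by the dosing text. The documents also do not say whether a patient infused on day 19 should drop the remaining sirolimus doses or take them alongside durvalumab.

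At stake is the order of treatment. Both co-primary objectives concern sirolimus followed by durvalumab. Section 3.1 gives the reason for the three-week lead-in: "In order to allow a reliable assessment of the contribution of sirolimus versus durvalumab to the observed clinical and PD outcome". Section 1.6.2 says that the risks of the combination are not known. An early first infusion blurs that sequence, and a short gap departs from the stated interval.

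**Working it through.** **Inputs.** C1 window 22 ± 3, C2 window 43 ± 3 and sirolimus days 1–21 come from the Day row. The last sirolimus dose on day 21 is also in Section 5.2.2. The 21-day cycle is in the synopsis and Section 3.1. Footnotes f and g of the schedule call Day 1 the first infusion day, but the Day row's own numbering is clear: days run from the first sirolimus dose.

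**The plan's own figure.** Nominal gap = 43 − 22 = 21 days, which agrees with every 3 weeks.

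**Windows.** C1: 22 − 3 = 19 to 22 + 3 = 25. C2: 43 − 3 = 40 to 43 + 3 = 46.

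**Sequence and gap, by C1 day.** Doses remaining = max(0, 21 − C1 day). Gap = 40 − C1 day to 46 − C1 day.

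| C1 on day | Sirolimus doses due on later days | In-window gap to C2 (days) |
|---|---|---|
| 19 | 2 | 21–27 |
| 20 | 1 | 20–26 |
| 21 | 0 | 19–25 |
| 22 | 0 | 18–24 |
| 23 | 0 | 17–23 |
| 24 | 0 | 16–22 |
| 25 | 0 | 15–21 |

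On days 19 and 20 the course is unfinished. On day 21 the last dose is taken that morning and can precede the infusion, so only the rule that C1 falls on the following day is broken.

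**Gap when the sequence is respected (C1 on days 22–25).** Shortest 40 − 25 = 15 days; longest 46 − 22 = 24 days. Of the 4 × 7 = 28 date pairs, 6 give a gap under 18 days: (23, 40), (24, 40), (24, 41), (25, 40), (25, 41) and (25, 42). These are counts of allowed dates, not probabilities, and the 18-day mark is the lower limit of the fix proposed here, not a limit in the plan.

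**Is there a C2 date that fits both texts?** Actual C1 + 21 gives 22 + 21 = 43 to 25 + 21 = 46, always in window. So the interval can be kept without leaving the schedule. For C1 on days 19–21, no choice of C2 date repairs the sequence.

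**After the fix.** Gap = 21 − 3 = 18 to 21 + 3 = 24 days. C2 falls on days 22 + 18 = 40 to 25 + 24 = 49.

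**The case against.** The strongest reply is that the dosing sections agree with one another: sirolimus through day 21, durvalumab from day 22, every 3 weeks. The ± 3 appears only in an assessment schedule and is an ordinary visit tolerance. A site that reads the whole protocol would give infusion 2 at 21 days from infusion 1, and that date is in window. This stands against one tempting inference, that the protocol authorises 15-day dosing; it does not, because the interval is stated repeatedly. It does not remove the conflict on the early side of the C1 window, where no reading satisfies both texts.

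Three further readings are tempting, and the documents do not support them.

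- *Footnote a leaves a late cycle 1 uncovered.* The footnote names only cycle 2. But with 21-day cycles a late C1 delays C2, which triggers the footnote, and Section 8.1 ties the other assessments to the dosing cycle. The wording deserves tidying but is not a separate defect.
- *An early C1 spoils the sirolimus trough.* Section 1.6.2.2 gives a half-life of about 62 h. From day 1 to day 19 is 18 × 24 = 432 h, and 432/62 ≈ 7 half-lives, after a loading dose. The level is then effectively at steady state.
- *The whole of days 19–21 precedes completion of sirolimus.* As shown above, that is secure only for days 19 and 20.

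Appendix 1, the study schema figure and the Appendix 6 flow sheets are not in the supplied text. Any of them could state an interval, and this could not be checked.

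**Conclusion.** The mismatch is real and small. As printed, the C1 window admits days 19 and 20, with 2 and 1 sirolimus doses still due on later days, and day 21, which is one day earlier than the dosing text allows. Because C2 is not tied to the actual C1 date, a gap of 15 days is in window against a stated 21. With C1 held to days 22–25, the in-window gap is 15–24 days.

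This rests on the Day row being counted from sirolimus day 1 and on the supplied text alone. The arithmetic is certain. How often a site would schedule such dates is unknown. A reader might infer that the efficacy conclusion is at risk. It is not: the pathologic complete response rule (at least 2 of 16, then at least 6 of 31), the one-sided alpha of 0.1, the power and the sample size do not depend on these windows. The matter is worth correcting at the next amendment.

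**What to change.** In the Day row:

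- C1 cell: *day 22 (+3 days; not before the day after the last sirolimus dose)*.
- C2 cell: *actual C1D1 + 21 days (± 3 days)*.

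As a conforming edit, let footnote a name a delay of either cycle.

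If C1 is late, draw the sirolimus trough on the day after the last sirolimus dose. Section 8.2.3 already implies this by asking for a separate appointment when durvalumab is delayed. It matters because a sample taken with a day-25 infusion would be 72 h later than the day-22 trough. With first-order decay (an assumption) and the half-life of 62 ± 16 h, it would read 0.5^(72/62) ≈ 45% of that trough (34% at 46 h, 53% at 78 h). Section 8.1.2 places the trough on day 23 and should be aligned with Section 8.2.3 in the same edit.

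**Cost.** Sites lose the three early days for C1. Infusion 2 may fall as late as day 49 instead of day 46, so surgery may be up to 49 − 46 = 3 days later in some patients. On the synopsis timing of two to three weeks after infusion 2, surgery would fall on days 40 + 14 = 54 to 49 + 21 = 70, within the span of the printed pre-surgery window (57 − 10 = 47 to 64 + 10 = 74). Section 3.1 allows up to four weeks, which would reach day 49 + 28 = 77, against 46 + 28 = 74 now.

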Appendix 3. American Joint Committee on Cancer Non-small cell Lung Cancer Staging, 8th Edition

Appendix 4. Information on Possible Drug Interactions

Appendix 5. Memory Aid for Heavy Water

Appendix 6. Trial Outline Patient Handouts

ABBREVIATIONS AND DEFINITION OF TERMS

The following abbreviations and special terms are used in this study Clinical Study Protocol.

Abbreviation or special term	Explanation
ADA	Anti-drug antibody

Abbreviation or special term	Explanation
ADCC	Antibody-dependent cell-mediated cytotoxicity
AE	Adverse event
AESI	Adverse event of special interest
ALP	Alkaline phosphatase
ALT	Alanine aminotransferase
APC	Antigen-presenting cells
AST	Aspartate aminotransferase
AUC	Area under the concentration-time curve
CDC	Complement-dependent cytotoxicity
CI	Confidence interval
CL	Clearance
C_{\max}	Peak concentration
$C_{\max,ss}$	Peak concentration at steady state
C_{\min}	Trough concentration
$C_{\min,ss}$	Trough concentration at steady state
CNS	Central nervous system
CR	Complete response
CT	Computed tomography
CTLA-4	Cytotoxic T-lymphocyte-associated antigen-4
DC	Disease control
DCR	Disease control rate
DLT	Dose-limiting toxicity
DNA	Deoxyribonucleic acid
DoR	Duration of response
ECG	Electrocardiogram
ECOG	Eastern Cooperative Oncology Group
EDTA	Disodium edetate dihydrate

Abbreviation or special term	Explanation
Fc	Fragment crystallizable
FFPE	Formalin fixed paraffin embedded
FSH	Follicle-stimulating hormone
FTIH	First-time-in-human
GCP	Good Clinical Practice
GMP	Good Manufacturing Practice
GLP	Good Laboratory Practice
HCl	Hydrochloride
HIV	Human immunodeficiency virus
ICF	Informed consent form
ICH	International Conference on Harmonization
IEC	Independent Ethics Committee
IFN	Interferon
IGF	Insulin-like growth factor
IgG1	Immunoglobulin G1
IgG2	Immunoglobulin G2
IGSF	Immunoglobulin superfamily
IHC	Immunohistochemistry
IL	Interleukin
imAE	Immune-mediated adverse event
IRB	Institutional Review Board
IV	Intravenous(ly)
MAb	Monoclonal antibody
MDSC	Myeloid-derived suppressor cells
MedDRA	Medical Dictionary for Regulatory Activities
miRNA	Micro ribonucleic acid
MRI	Magnetic resonance imaging

Abbreviation or special term	Explanation
mRNA	Messenger ribonucleic acid
MTD	Maximum tolerated dose
NCI CTCAE	National Cancer Institute Common Terminology Criteria for Adverse Events
NK	Natural killer
NOAEL	No-observed-adverse-effect level
NSCLC	Non-small cell lung cancer
OR	Objective response
ORR	Objective response rate
OS	Overall survival
PBMC	Peripheral blood mononuclear cell
PD	Progressive disease
PD-1	Programmed cell death 1
PD-L1	Programmed cell death ligand 1
PD-L2	Programmed cell death ligand 2
PFS	Progression-free survival
PK	Pharmacokinetic(s)
PR	Partial response
PRO	Patient-reported outcome
PVC	Polyvinyl chloride
Q2W	Every 2 weeks
Q3M	Every 3 months
Q3W	Every 3 weeks
Q4W	Every 4 weeks
Q12W	Every 12 weeks
QoL	Quality of life

Abbreviation or special term	Explanation
QTc	Time between the start of the Q wave and the end of the T wave corrected for heart rate
QTcF	QT interval on ECG corrected using the Frederica's formula
RCC	Renal cell carcinoma
RECIST	Response Evaluation Criteria in Solid Tumors
RNA	Ribonucleic acid
SAE	Serious adverse event
SD	Stable disease
SID	Subject identification
sPD-L1	Soluble programmed cell death ligand 1
SOCS3	Suppressor of cytokine signaling 3
SUSAR	Suspected unexpected serious adverse reaction
$t_{1/2}$	Half life
TEAE	Treatment-emergent adverse event
TIL	Tumor infiltrating lymphocyte
T_{max}	Time to peak concentration
$T_{max,ss}$	Time to peak concentration at steady state
TNF- α	Tumor necrosis factor alpha
TSH	Thyroid stimulating hormone
ULN	Upper limit of normal
USA	United States of America
WFI	Water for injection
WHO	World Health Organization

